## **2.6 Safety Analyses**

Safety evaluations will be based on the incidence, intensity, and type of adverse events (AEs), and changes in vital signs. Safety summaries will be presented for all patients in the safety population.

### **2.6.1 Adverse Events**

AEs that occur through the TOC Visit will be summarized by System Organ Class (SOC), Preferred Term, intensity, and treatment group for treatment-emergent AEs. Summaries will also be provided for study drug-related AEs, serious AEs, and AEs leading to study discontinuation. Each patient will be counted only once for each of the incidence rates, regardless of the number of occurrences (events) the patient experiences.

A Treatment-emergent AE is defined as any AE that occurs after administration of the study drug and through the final visit, or any event that is considered study drug-related regardless of the start date of the event.

	SEC-WH-301 Statistical Analysis Plan	Revision No.: 2.0
	Document Date: 20-Mar-2020	Page 11 of 12

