4. STUDY OBJECTIVES

4.1 PRIMARY OBJECTIVE(S)

The objective of this study is to evaluate the efficacy and safety of a single, oral dose of Solosec containing 2 grams of secnidazole compared to placebo for the treatment of trichomoniasis.

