11. DATA COLLECTION AND ANALYSIS

This section describes the biostatistical analysis as foreseen at the time of planning the study. Changes, additions and further details about the analyses will be described in the Statistical Analysis Plan (SAP). After finalization of the SAP and unblinding, any additional analyses or changes to analyses that may be required will be fully disclosed in the clinical trial report.

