11.5.2 Safety Analyses

Safety evaluations will be based on the incidence, intensity, and type of AEs. Safety variables will be tabulated and presented for all patients in the Safety population.

Summarization will focus on incidence of SAEs; treatment-emergent AEs by System Organ Class (SOC) and Preferred term; AEs that are considered study-drug related; and AEs leading to study discontinuation.

Adverse events will be coded using the Medical Dictionary for Regulatory Activities (MedDRA) for purposes of summarization.

A Treatment-emergent AE is defined as any AE that occurs after administration of the study drug and through the final visit, any event that is considered study drug-related regardless of the start date of the event, or any event that is present at baseline but worsens in intensity or is subsequently considered study drug-related by the Investigator.

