## 2. STATISTICAL METHODOLOGY

### 2.1 General Principles

All analyses will be performed using SAS® software version 9.4. Prior and concomitant medications will be coded using World Health Organization (WHO) Drug Dictionary Enhanced March 2019. Medical history and Adverse Events (AEs) will be coded using Medical Dictionary for Regulatory Activities (MedDRA) version 22.0.

Continuous variables will be summarized by n (number of patients with non-missing results), mean, standard deviation (SD), median, minimum, and maximum. Categorical variables will be summarized by count and percent (of patients in the population with a non-missing result).

All data collected will be presented in data listings. Data collected subsequent to TOC (Visits 3 and 4) will be included in data listings but will not be used for any analyses.

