## 2.3 Study Populations

**Intent-to-Treat (ITT):** The ITT population will include all randomized patients. Patients will be summarized based on the randomized treatment group.

**Modified Intent-To-Treat (mITT):** The mITT population will include all randomized patients who were culture positive for *T. vaginalis* and negative for STIs (lab results will not be known until after randomization). Patients will be summarized based on the randomized treatment group.

**Per-Protocol (PP):** The PP population will be composed of patients in the mITT population with consideration of the following criteria: received the study medication as randomized, met inclusion and exclusion criteria, had a TOC visit between Days 6-12, and had no major protocol violations. The composition of the PP population will be finalized and documented in a review of the data conducted prior to unblinding the study database.

**Safety:** The Safety population will be composed of all randomized patients who received any amount of study medication. Patients will be summarized based on the treatment group actually received.

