#### **4 CHANGES FROM THE PROTOCOL**

This analysis plan clarifies that data subsequent to the TOC visit (Visits 3 and 4) will be included in data listings but will not be used in any analyses.

This analysis plan clarifies that the presence/absence of clinical symptoms of trichomoniasis is based on symptoms reported during the baseline vaginal assessment, with a sensitivity analysis if this differs from the randomized strata.

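### Adverse events after placebo patients' delayed Solosec dose have no specified incidence summary; one labelled descriptive table would close the gap

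*SAP*

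**What the plan says.** SAP 2.6.1 sets the main safety table: "AEs that occur through the TOC Visit will be summarized by System Organ Class (SOC", then Preferred Term, intensity and treatment group. Its next sentence promises summaries of drug-related AEs, serious AEs and AEs leading to discontinuation, without repeating the TOC limit. The same section defines a treatment-emergent AE over a longer window, as "any AE that occurs after administration of the study drug and through the final visit", and adds drug-related events whatever their start date.

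SAP 2.1 states: "Data collected subsequent to TOC (Visits 3 and 4) will be included in data listings but will not be used for any analyses". SAP 4 discloses this as a clarification of the protocol: "data subsequent to the TOC visit (Visits 3 and 4) will be included in data listings but will not be used in any analyses". Protocol 11.5.2 says "Safety variables will be tabulated and presented for all patients in the Safety population" and has no TOC cut-off.

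SAP 2.3 assigns the Safety population as follows: "Patients will be summarized based on the treatment group actually received". It does not say how this works for a patient who takes both treatments. Under Protocol 5.1 and 9.3.2, that is every patient dosed at both visits: the opposite treatment follows completion of the Visit 2 procedures.

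Safety follow-up continues after that dose. Patients who are culture-positive at Visit 2 return for Visit 3 after 7–12 days (Protocol 9.3.3). Culture-negative patients get a telephone contact that covers safety, with no stated timing, and an unscheduled visit if they report an AE (Protocol 9.3.2 and 9.3.4).

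**The concern.** For a placebo patient, the Visit 2 dose is the study drug in the target population. The AEs that follow it bear directly on Solosec in trichomoniasis, and the trial collects them. Because the dose comes after the TOC procedures, the SOC and Preferred Term table stops just before these exposures begin. A listing shows the events but gives no denominator or rate.

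The SAP also defines treatment emergence over a wider window than it summarises. Read literally, even that definition reaches past TOC only for patients with a later visit. For a culture-negative patient followed only by telephone, Visit 2 is the last visit. At stake is the precision of the AE rates for Solosec in this indication.

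**Working it through.** **Inputs.** About 144 patients, randomised 1:1 (Protocol 5.1). Planned mITT yield 70%, and assumed placebo cure rate 40% in mITT (Protocol 11.2; SAP 2.2). Unknown cure status counts as not cured (Protocol 11.6.4; SAP 3.2). The documents state no number of Solosec exposures and no Visit 2 dosing rate.

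**The plan's own figure.** 100 / 0.70 = 142.9, so 143, or 144 for equal arms. This reproduces the stated enrolment and gives 144 / 2 = 72 per arm.

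**Share of Solosec exposures left out.** Let f be the fraction of placebo patients dosed at Visit 2 (assumption). Delayed doses = 72f; share = 72f / (72 + 72f).

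| f | Delayed doses | All Solosec exposures | Share |
|---|---|---|---|
| 50% | 36 | 108 | 33.3% |
| 70% | 50.4 | 122.4 | 41.2% |
| 80% | 57.6 | 129.6 | 44.4% |
| 90% | 64.8 | 136.8 | 47.4% |
| 100% | 72 | 144 | 50.0% |

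**How the delayed doses are followed.** Clinic Visit 3 count = dosed × share culture-positive at baseline × share of those still positive at Visit 2. The baseline share is taken as 70–100% (assumption; 70% is the mITT yield, which also requires negative STI results). Patients who are culture-negative at baseline are assumed to stay negative.

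- 40% cure rate applied to those who attend, so 60% still positive. At f = 80%: 57.6 × 0.7 × 0.6 = 24.2 to 57.6 × 1.0 × 0.6 = 34.6. At f = 100%: 72 × 0.7 × 0.6 = 30.2 to 72 × 1.0 × 0.6 = 43.2.
- 40% cure rate counting missing as not cured, with the undosed 20% having no TOC result. All cures then fall among attendees, whose positive share is 1 − 0.40/0.80 = 50%. At f = 80%: 57.6 × 0.7 × 0.5 = 20.2 to 57.6 × 1.0 × 0.5 = 28.8.

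For f of 80–100%, this gives about 20–43 with a clinic visit. Telephone only is the remainder, from 57.6 − 34.6 = 23.0 to 72 − 30.2 = 41.8, so about 23–42.

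**What the extra exposures add.** Exact two-sided 95% upper limit with zero events = 1 − 0.025^(1/n):

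- TOC-limited table, n = 72: 5.0%.
- Adding only delayed doses with a clinic visit, n = 72 + 20 = 92 to 72 + 43 = 115: 3.9% to 3.2%.
- Adding all delayed doses, n = 130 to 144: 2.8% to 2.5%. This is a best case, since it needs telephone contact to find AEs as well as a clinic visit does.

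**The case against.** The strongest reply is that this is a preference and not an error. The cut-off is deliberate and disclosed in SAP 4. Protocol 11 provides that "Changes, additions and further details about the analyses will be described in the Statistical Analysis Plan (SAP", and the objective is efficacy and safety "compared to placebo for the treatment of trichomoniasis". After Visit 2 no group is on placebo alone, so ending the randomised comparison there is right. No objective or endpoint is tied to the follow-up phase, and with about 144 patients events could be counted from the listings. Protocol 3.2.1 already reports 518 women with bacterial vaginosis given this dose. All of that stands. It limits the point to precision in trichomoniasis and to the usefulness of a rate over a listing.

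A reader might go further in three ways that the documents do not support:

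- **That no AE after the delayed dose can reach any summary.** The wording is less clear than that. The sentence on related, serious and discontinuation AEs does not repeat the TOC limit, and the parenthesis in SAP 2.1 and 4 names Visits 3 and 4 but not telephone or unscheduled contacts. Exclusion is the likelier reading. What can be said firmly is that no post-TOC summary is specified.
- **That events after the switch will be credited to the wrong arm.** The TOC cut-off works as an implicit period rule. Only an event starting on the Visit 2 day after the second dose is ambiguous. That is close to hypothetical, because the AE query opens the visit and dosing closes it.
- **That safety data are lost.** They are listed, and serious AEs reach the sponsor within 24 hours (Protocol 10.6).

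**Conclusion.** The point holds as a minor, cheap improvement. AEs after the placebo group's delayed Solosec dose have no specified incidence summary. On planned enrolment that leaves out about 44–50% of Solosec exposures if 80–100% of placebo patients are dosed at Visit 2, and about 33–41% if 50–70% are. Both ranges rest on assumed dosing rates.

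The firmer gain in precision is the one from delayed doses with a clinic visit (zero-event bound from 5.0% to about 3.9–3.2%). The clinic and telephone counts depend further on the baseline culture-positive share and on whether the 40% cure rate counts missing as not cured.

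A reader might infer that the SAP breaches the protocol, or that the TOC cut-off should go. Neither follows: the protocol allows the change, and the cut-off protects the randomised comparison. Primary efficacy, sample size and the placebo-controlled safety comparison are untouched, so nothing supports a rating above minor.

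**What to change.** Keep the randomised AE comparison through TOC as planned, and make these changes to the SAP:

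1. Add one descriptive follow-up-phase table of treatment-emergent, serious and related AEs and AEs leading to discontinuation. It runs from the Visit 2 dose to final contact, including telephone and unscheduled contacts, by treatment taken at Visit 2.
2. Label it as not for comparing arms, and show how many patients were followed by clinic visit and how many by telephone only. Any summary of all Solosec exposures should show the two periods separately as well as combined.
3. State that an event starting after the second dose on the Visit 2 day belongs to the follow-up table. Use recorded onset and dose times where available, and a stated convention otherwise. Protocol 10.4 records AE onset date and time, but Protocol 7.6 asks only for the date of administration.
4. Amend the sentences in SAP 2.1 and 4 that bar use of post-TOC data so that they allow this table.

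The cost is SAP wording and a few more tables; the AE data are already collected. The drawback is that follow-up after Visit 2 is uneven and depends on the culture result, which is why the descriptive label and the counts in item 2 are needed.

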9.3.2 Visit 2/Test of Cure Visit (Study Day 6-12)

The Test of Cure (TOC) Visit should be conducted between Study Day 6 and 12.

The following procedures will be performed at the TOC Visit:

1. Assess for adverse events;
2. Review and record concomitant medications/treatments taken during the study;
3. Perform a urine pregnancy test;
4. Perform a targeted physical examination as needed to assess AEs. Collect vital signs;
5. Perform a pelvic examination including assessment of vaginal discharge, and collection of vaginal samples as follows:
 - a. Perform clinical assessment of trichomoniasis genital symptoms (e.g., itching, discharge, odor).
 - b. Collect vaginal sample for *T. vaginalis* testing via:
 - i. BioMed InPouch™ TV test.

Upon completion of the primary phase (Visit 1 (baseline) to Visit 2 (Day 6-12)), the site will use IWRS to receive the Visit 2 kit number for the opposite treatment (placebo patients will receive Solosec and vice versa). Study treatment will be provided for the follow-up phase as described in section in Section 7 of the protocol.

The following procedures will be performed after the patient has been successfully completed the Day 6-12 TOC procedures described above:

1. The patient will self-administer the study medication (without regard to meals). (See Section 7.1 for drug administration instructions).

Patients with negative cultures for *T. vaginalis* at Visit 2 (i.e., negative InPouch™ TV test) will be contacted by phone and discharged from the study (no Visit 3 required). Note: The telephone contact will include an assessment of safety and well-being. Subjects reporting any complaints, or an adverse event will be asked to return for an unscheduled visit for evaluation and safety assessment.

A follow-up visit will be scheduled for all patients who have positive cultures for *T. vaginalis* (i.e., positive InPouch™ TV test at Visit 2).

Note: patients who are subsequently found to have a negative culture for *T. vaginalis* (i.e., negative InPouch™ TV test) from the sample obtained at the Baseline Visit (Day 1) should remain in the study and complete all appropriate study visits.

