10.4 RECORDING OF ADVERSE EVENTS

Adverse Events are illnesses or signs/symptoms that appear or worsen during the testing of a drug whether or not considered related to the investigational product (synonyms = medicinal or pharmaceutical product, study drug, clinical trial materials, etc.), including side effects, injury, toxicity, or hypersensitivity reactions.

All adverse events, including observed, elicited, or volunteered problems, complaints or symptoms, are to be recorded on the Adverse Events page in the subject’s Case Report Form.

The need to capture this information is not dependent upon whether adverse events are associated with use of the investigational product.

Adverse events resulting from concurrent illnesses, reactions to concurrent illnesses, reactions to concurrent medications progression of disease states should also be recorded. In order to avoid vague, ambiguous or colloquial expressions, adverse events should be recorded in standard medical terminology rather than the subject’s own words. Signs and symptoms should be reported individually unless, in the judgment of the investigator, they can be grouped under an inclusive term (e.g., gastroenteritis in lieu of abdominal pain, nausea, vomiting, and diarrhea).

Each adverse event is to be evaluated for date/time of onset, duration, intensity, and causal relationship with the investigational product or other factors.

At every study visit, the investigator must document new AEs and the outcome of ongoing AEs. Any subject with an AE (including SAEs) or any clinically significant abnormal laboratory result or physical finding reported as an AE will be followed by the investigator until the AE resolves, resolves with sequelae, is otherwise explained by a medical condition, follow-up is not possible (document), or the subject dies.

10.4.1 Clinical Laboratory Abnormalities and Other Abnormal Assessments as AE:

Clinically significant abnormal laboratory findings or clinically significant abnormal findings from other assessments that are detected during the study or are present at baseline and significantly worsen following the start of the study will be reported as AEs. Abnormal laboratory findings or other assessments deemed as abnormal will not be reported as AEs if they are determined to be clinically insignificant.

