### 1.2 Study Design

This is a Phase 3, multi-center, prospective, randomized, placebo-controlled, delayed treatment, double-blind, study to evaluate the effectiveness, and safety of a single, oral dose of Solosec containing 2 grams of secnidazole in female patients with trichomoniasis. Approximately 144 patients who test positive for trichomonas on OSOM® rapid test or via wet mount assessment or have positive *Trichomonas vaginalis* (*T. vaginalis*, TV) Nucleic Acid Amplification Testing (NAAT) within 30 days of screening (and have not been treated) and fulfill other eligibility criteria at the baseline visit will be enrolled in this study. The diagnosis of *T. vaginalis* will be confirmed by a positive culture for *T. vaginalis*.

The study will consist of a primary study phase (Visit 1 (baseline) to Visit 2 (Day 6-12)) and a follow-up phase (Visit 2 to Visit 3 (7-12 days post Visit 2)). During the primary phase patients will be randomly assigned in a 1:1 ratio to either Solosec or placebo. The randomization will be stratified by site and based on the clinical symptoms of trichomoniasis (present or absent).

Patients will return to the clinic for the “test of cure” (TOC) visit to be conducted on Days 6-12 (Visit 2). After all Visit 2 (V2) study procedures have been completed, patients will receive the opposite treatment (placebo patients will receive Solosec and vice versa). Patients with V2 cultures that are subsequently positive for *T. vaginalis* will return to the clinic for Visit 3 (V3) assessments and investigator assessment of need for additional therapy (an additional Visit 4 may be scheduled at the investigator’s discretion if culture at V3 is positive). Patients with

	SEC-WH-301 Statistical Analysis Plan	Revision No.: 2.0
	Document Date: 20-Mar-2020	Page 8 of 12

cultures that are negative at V2 will be contacted by phone and discharged from the study (no V3 required).

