# 3. DATA HANDLING

## 3.1 Baseline and Study Visits

Visits for all analyses will be as recorded on the Case Report Form (CRF). Baseline is defined as the last assessment (including unscheduled assessments) prior to dosing. The day of dosing is considered Day 1. Assessments will be considered Baseline if the assessment is before the date of dosing, or if the assessment was done on Day 1 and, according to the Study Schedule of Assessments, was supposed to be performed on Day 1 prior to treatment.

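### SAP 2.6.1 ends the adverse-event comparison at the TOC visit, not before the crossover dose taken there, so events after that dose can be tabulated under the opposite treatment

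*SAP*

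**What the plan says.** The comparative AE tables are defined in SAP 2.6.1: "AEs that occur through the TOC Visit will be summarized by System Organ Class (SOC), Preferred Term, intensity, and treatment group for treatment-emergent AEs". Summaries of drug-related AEs, serious AEs and AEs leading to discontinuation follow in the same paragraph. The next paragraph defines treatment emergence: "A Treatment-emergent AE is defined as any AE that occurs after administration of the study drug and through the final visit". It does not say which of the two doses is meant.

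SAP 1.2 puts the second dose at the visit that closes this window: "After all Visit 2 (V2) study procedures have been completed, patients will receive the opposite treatment (placebo patients will receive Solosec and vice versa". Protocol 9.3.2 gives the order of events at that visit. The first listed procedure is "Assess for adverse events". After the TOC procedures, "the site will use IWRS to receive the Visit 2 kit number for the opposite treatment (placebo patients will receive Solosec and vice versa"), and the patient takes the dose. Protocol 7.1 requires each dose to be witnessed and documented.

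Four other provisions bear on the point:

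- SAP 2.3, on the Safety population: "Patients will be summarized based on the treatment group actually received".
- SAP 2.1 and SAP section 4: data collected after TOC go into listings and not into analyses. Both places identify those data as Visits 3 and 4.
- SAP 3.1: "Visits for all analyses will be as recorded on the Case Report Form (CRF").
- Protocol 10.4: "Each adverse event is to be evaluated for date/time of onset, duration, intensity, and causal relationship with the investigational product or other factors".

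**The concern.** The window is described by a visit, and the treatment changes during that visit. An AE that starts an hour after the crossover dose has an onset date equal to the TOC visit date. On a date-based or visit-based cut it belongs to the window, and it is tabulated under the treatment given at Visit 1. A reaction to Solosec in a placebo-first patient then appears as a placebo AE, and a reaction to placebo in a Solosec-first patient appears under Solosec. The as-received rule in SAP 2.3 does not settle the matter, because a patient who has taken the Visit 2 dose has received both treatments.

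The study objective includes safety compared with placebo, and these are the only between-group AE tables. Protocol 3.2.1 names nausea, headache and dysgeusia as the common reactions to a single Solosec dose. It gives no onset times, but reactions of this kind can plausibly start on the day of dosing. Moving such events into the other group shrinks the Solosec-minus-placebo difference, which is the unsafe direction for a safety table.

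**Working it through.** The documents state no AE rate by day or by group, so there is no planned figure to reproduce. The check has two parts: which events the text lets into the table, and what their entry does to the difference.

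**Part 1. Routes into the table for an AE that starts on the Visit 2 date after the second dose**

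- *Seen on site after the witnessed dose.* This is Visit 2 data under SAP 3.1. The listings-only rule does not reach it.
- *Reported at the telephone contact.* Protocol 9.3.2 gives this contact, with a safety assessment, to patients who are culture-negative at Visit 2. It is neither Visit 3 nor Visit 4, so the rule in SAP 2.1 and section 4 does not name it.
- *Reported at an unscheduled visit (Protocol 9.3.4).* This is also not named by the rule.
- *First collected at Visit 3 or 4.* This is listed only under SAP 2.1 and section 4. It enters the table only if the programmer selects by onset date alone, which the verb in SAP 2.6.1 (when AEs occur, not when they are collected) would allow.

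**Part 2. Effect on the difference**

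Inputs, all assumed: d and b are the dosing-day AE incidences on Solosec and placebo, c is the incidence of other AEs (equal in both groups), and f is the share of crossover-day AEs that enter the table. For f to be high, the dose must be taken, the event must be reported, and it must then be assigned to the first-dose group.

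- Solosec-first rate = 1 - (1 - d)(1 - c)(1 - f·b)
- Placebo-first rate = 1 - (1 - b)(1 - c)(1 - f·d)
- Subtracting, difference = (1 - c)(d - b)(1 - f)

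In this model the share of the dosing-day excess that is kept is therefore 1 - f.

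With d = 10%, b = 2%, c = 5%:

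| f | Solosec-first | Placebo-first | Difference (points) |
|---|---|---|---|
| 0 | 1 - 0.90 × 0.95 = 14.5% | 1 - 0.98 × 0.95 = 6.9% | 7.6 |
| 0.5 | 1 - 0.855 × 0.990 = 15.4% | 1 - 0.931 × 0.95 = 11.6% | 3.8 |
| 0.8 | 1 - 0.855 × 0.984 = 15.9% | 1 - 0.931 × 0.92 = 14.3% | 1.5 |
| 1 | 1 - 0.855 × 0.98 = 16.2% | 1 - 0.931 × 0.90 = 16.2% | 0 |

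With d = 5%, b = 1%, c = 5%, the difference is 0.95 × 4 = 3.8 points at f = 0, 0.8 at f = 0.8 and 0 at f = 1.

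If only a share w of the Solosec excess falls on the dosing day, the share of the total excess kept is about 1 - w·f on an additive scale. With w = 0.5 that is 75% at f = 0.5 and 50% at f = 1.

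**An intermediate case.** Suppose the listings-only rule is applied to everything collected at Visits 3 and 4, and the telephone contact is the only open route. Under the plan's sample-size assumptions (SAP 2.2, mITT patients), about 75% of Solosec-first and 40% of placebo-first patients are culture-negative at Visit 2 and so are telephoned. Assume that all of their crossover-day AEs are reported and counted. The rates are then 1 - 0.855 × (1 - 0.75 × 0.02) = 15.8% and 1 - 0.931 × (1 - 0.40 × 0.10) = 10.6%. The difference is 5.2 points, or 68% of the 7.6 points. This is an illustration only; the Safety population also contains patients outside the mITT set.

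**The case against.** A reader might infer that the plan does count crossover-day AEs under the wrong treatment and that Solosec's dosing-day excess is largely cancelled. The documents do not support that, for these reasons:

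- The AE query is the first procedure at Visit 2 and the second dose comes last. The protocol also says the opposite treatment is given on completion of the primary phase. The window can fairly be read as closing at that query, before the dose. No passage sets a cut-off at the end of the calendar day.
- AEs first collected at Visit 3 or 4 are expressly kept out of the analyses, and SAP section 4 repeats this as a deliberate clarification. Assigning visits as recorded on the CRF also favours selection by collection visit.
- If the analysis is confined to the primary phase, each patient has one treatment, and the as-received grouping causes no difficulty.
- Near-complete cancellation needs f close to 1 and an excess concentrated on the dosing day. The documents give no onset timing, no AE rates and no capture rate. At f = 0 nothing is lost.
- The AE tables are descriptive, vital signs are also summarised by group (SAP 2.6.2), and the listings would still show every event.

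These points stand and limit the claim. They do not close the gap. SAP 2.6.1 selects by when an AE occurs, states no cut at the second dose, and relies on an exclusion that names only Visits 3 and 4. On-site events after the Visit 2 dose, telephone reports and unscheduled visits stay open. Two programmers following this text could produce different AE tables.

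**Conclusion.** The point holds as an ambiguity with a known direction, not as a demonstrated error. The AE window includes the visit at which treatment is switched, and no rule ends it at the second dose. Applied by onset date or visit date, it places post-crossover events under the first-dose group and moves the only between-group AE comparison toward no difference. The exposure is limited to post-dose events recorded at Visit 2, by telephone or at unscheduled visits, unless selection is by onset date alone.

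The size cannot be fixed from the documents. About 1 - f of a dosing-day excess is kept: all of it at f = 0, half at f = 0.5, none at f = 1. The 7.6, 1.5 and 0 point differences rest on assumed rates and on equal f in both groups. AEs that start on other days before the second dose are unaffected. This should be fixed before unblinding. It does not affect the primary efficacy analysis.

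**What to change.** - **SAP 2.6.1.** Define the comparison as treatment-emergent AEs with onset after the Visit 1 dose and before the Visit 2 dose, judged by onset date and time against the Visit 2 dosing date and time. If the onset is on the Visit 2 date and the time is missing, treat the AE as post-dose when it was first recorded after the pre-dose AE query.
- **SAP 2.6.1.** Tabulate or list AEs with onset at or after the Visit 2 dose separately, under the treatment given at Visit 2, whatever the route by which they were reported.
- **SAP 2.3.** State that, for the safety comparison, the treatment received means the treatment received at Visit 1.

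The cost is SAP wording and one programming condition, with no added patients or visits. Onset date and time are already to be evaluated for each AE (Protocol 10.4), and each dose is witnessed and documented (Protocol 7.1). The one dependency is the Visit 2 dosing time. Protocol 7.6 mentions only the date of administration, so the sponsor should confirm that the time is available in the eCRF or source documents.
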